In this hierarchical testing structure, each hypothesis is tested at a significance level of 0.05, two-sided. Statistical significance at each step is required in order to test the next hypothesis. If the primary endpoint meets the criteria for statistical significance, then the percent change from baseline to Week 24 in LDL-C will be tested; and so forth.

For the remaining secondary efficacy endpoints and the tertiary efficacy endpoints, a significance level of 0.05 will be used; given the large number of remaining endpoints, the p-values for those endpoints will be considered descriptive.

Percent change from baseline to Week 24 in LDL-C; change from baseline to Weeks 12 and 24 in LDL-C; percent change from baseline to Weeks 12 [REDACTED] in [REDACTED] non-HDL-C, [REDACTED] TC, apoB, and

hs-CRP will each be analyzed using ANCOVA with treatment group and patient type (primary prevention; secondary prevention) as factors and the relevant baseline as a covariate. Baseline for [REDACTED] non-HDL-C, [REDACTED] and TC will be defined as the mean of the lipid values from Week -1 (Visit S3) and predose Day 1/Week 0 (Visit T1). Baseline for apoB and hs-CRP will be defined as the predose Day 1/Week 0 (Visit T1) value. Each ANCOVA will be performed using the FAS, with patients included in their randomized treatment group regardless of the treatment they actually received. Only observed case data will be included in each analysis (no imputation will be performed for missing data). For each lipid parameter and analysis time point, the LSM and SE will be provided for both treatment groups, along with the placebo-corrected LSM, its 95% CI and associated p-value.

For all continuous efficacy endpoints (percent change from baseline in LDL-C, [REDACTED] non-HDL-C, TC, [REDACTED] apoB, and hs-CRP; change from baseline in LDL-C; to Weeks 12 and 24, as appropriate), the ANCOVA assumption of normality will be assessed. If non-normality of the data is found at any time point for any parameter, either the data will be transformed so that it is normally distributed or a nonparametric test will be used instead of the planned ANCOVA.

Additional Post-randomization Adjunctive Triglyceride-lowering Therapy:

The number and percent of patients in each treatment group requiring additional (post-randomization) TG-lowering therapy will be summarized. The medications will be summarized by treatment group.

Safety Analyses

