Each ANCOVA will be performed using the FAS, with patients included in their randomized treatment group regardless of the treatment they actually received. Same imputation method described for the primary endpoint will be used for those secondary endpoints included in the step-down procedure, while only observed data analysis will be used for other secondary and tertiary endpoints. For each lipid parameter and analysis time point, the LSM and SE will be provided for both treatment groups, along with the placebo-corrected LSM, its 95% CI and associated p-value.

The ANCOVA assumption of normality will be assessed. If severe non-normality of the data is found at any time point for any parameter, either the data will be transformed so that it is normally distributed or a nonparametric test will be considered instead of the planned ANCOVA.

Finally, the number and percent of patients in each treatment group requiring additional (post-randomization) TG-lowering therapy will be summarized. The medications will be summarized by treatment group.

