### 3. STUDY DESIGN

#### 3.1. GENERAL DESCRIPTION

This is a Phase 3, randomized, double-blind, placebo-controlled, parallel group multicenter study that will be conducted at approximately 71 clinical sites in North America. Screening Week -5 (Visit S1) will be approximately 5 weeks prior to randomization. Eligible patients will return to the clinical site at Week -4 (Visit S2) to initiate administration of single-blind (patient only) placebo study drug. Eligible patients will return at Week -1 (Visit S3) for lipid and safety laboratories and an assessment of tolerability and study drug adherence. Approximately 300 patients with a history of statin intolerance (SI) will be stratified based on patient type (primary prevention; secondary prevention) and randomized at Week 0 (Visit T1) in a 2:1 ratio to receive either bempedoic acid 180 mg (n = 200) or matching placebo (n = 100) once daily for 24 weeks. Randomized patients will return for clinic visits at Week 4 (Visit T2), Week 12 (Visit T4), and Week 24 (Visit T5). A phone visit will occur at Week 8 (Visit T3).

Figure A 1002-046 Study Design

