## 7.2. ADJUSTMENTS FOR COVARIATES AND FACTORS TO BE INCLUDED IN ANALYSES

The following covariates and factors are used in the analyses. For details of their inclusion in the models, see the specific analysis section.

- treatment group (bempedoic acid 180 mg/day; placebo)
- baseline laboratory value of interest
- CVD risk category (primary prevention; secondary prevention)
- treatment by subgroup interaction term for subgroup analyses of efficacy variables

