## 7.5. MULTIPLE COMPARISONS/ MULTIPLICITY

In terms of controlling the overall Type I error rate, a gatekeeping or stepdown approach will be used to test the primary efficacy endpoint and then specific secondary efficacy endpoints sequentially in order to preserve the study-wise Type I error rate. The sequence for the stepdown procedure in this study is as follows:

1. Test the primary efficacy endpoint: percent change from baseline to Week 12 in LDL-C
2. Test the percent change from baseline to Week 24 in LDL-C
3. Test the percent change from baseline to Week 12 in non-HDL-C
4. Test the percent change from baseline to Week 12 in TC
5. Test the percent change from baseline to Week 12 in apoB
6. Test the percent change from baseline to Week 12 in hsCRP

In this hierarchical testing structure, each hypothesis is tested at a significance level of 0.05, two-sided. Statistical significance at each step is required in order to test the next hypothesis. If the primary endpoint meets the criteria for statistical significance, then the percent change from

[REDACTED]

[figure not shown]
Version Number: 1.7  
 Version Date: 21Mar2018

[REDACTED]

baseline to Week 24 in LDL-C will be tested; and so forth.

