**18.2.1. KEY SECONDARY EFFICACY VARIABLES & DERIVATIONS**

The key secondary endpoints, which are included in the hierarchical analysis described in [Section 7.5](#), are:

- percent change from baseline to Week 24 in LDL-C
- percent change from baseline to Week 12 in non-HDL-C
- percent change from baseline to Week 12 in TC
- percent change from baseline to Week 12 in apoB
- percent change from baseline to Week 12 in hsCRP.

Key secondary endpoints of LDL-C, non-HDL-C, TC, and apoB will be analyzed using the same ANCOVA model described in 18.1.2.

Similar to the primary endpoint, missing data will be imputed using multiple imputation method as described in 18.1.3.

For hsCRP, a non-parametric (Wilcoxon rank-sum test) analysis with Hodges-Lehmann estimates and confidence interval will be performed because based on historical knowledge, publication precedence (Brendan etc., 2006) and recent data available, hsCRP is known to be skewed by extreme values and have non-normal distribution.

Graphic presentations (mean+/-SE) or median (IQR) for efficacy parameters will be provided.

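### The confirmatory hsCRP test in SAP 18.2.1 is valid but is not adjusted for baseline hsCRP or patient type, so it gives up some power

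*SAP*

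**What the plan says.** SAP 7.5 places hsCRP sixth and last in the step-down sequence ("Test the percent change from baseline to Week 12 in hsCRP"), and there "each hypothesis is tested at a significance level of 0.05, two-sided". SAP 18.2.1 sends the other four key secondary endpoints to the ANCOVA of 18.1.2, which adjusts for patient type and baseline. For hsCRP it departs from this: "For hsCRP, a non-parametric (Wilcoxon rank-sum test) analysis with Hodges-Lehmann estimates and confidence interval will be performed". The reason given is skewness and extreme values. No stratified version and no covariate is named.

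The protocol synopsis planned that the secondary endpoints, down to "hs-CRP will each be analyzed using ANCOVA with treatment group and patient type (primary prevention; secondary prevention) as factors and the relevant baseline", would share one adjusted model. Protocol 11.6 adds that under severe non-normality "either the data will be transformed so that it is normally distributed or a nonparametric test will be considered instead of the planned ANCOVA". It defines baseline hs-CRP as the single predose value at Visit T1. SAP 7.2 lists the "baseline laboratory value of interest" and the CVD risk category among its covariates and factors, but leaves their use to each analysis section. Section 18.2.1 does not take them up for hsCRP.

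**The concern.** Skewness is a reason to move to ranks or logs. It is not by itself a reason to drop covariates, because a rank analysis can carry them.

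Percent change divides by baseline, but that is not the same as adjusting for it. Patients with a high single baseline value tend to fall, and those with a low value tend to rise, whatever their treatment. An unadjusted test leaves that predictable variation in the comparison. At stake is the chance of detecting a real hsCRP effect at a step that supports a confirmatory claim, with a planned placebo group of only 100.

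**Working it through.** **Inputs from the documents.** About 300 patients randomized 2:1 (SAP 3.1): 300 × 2/3 = 200 and 300 × 1/3 = 100, as stated. Two-sided alpha is 0.05 (SAP 7.5). No power, effect size or SD for hsCRP is given, so there is no planned figure to reproduce.

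**Assumed inputs, not in the documents.** Correlation ρ between log baseline and log Week 12 hsCRP of 0.3 to 0.8; equal log-scale SD s at both visits; 40% of patients in one stratum; complete data; effect sizes as stated below.

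**Step 1: what the plain test works on.** Let d = log(Week 12/baseline). Percent change is 100(e^d − 1), which increases with d, so its ranks are the ranks of d. The test therefore acts on an unadjusted log change score.

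**Step 2: variance.**
- Unadjusted change: 2s²(1 − ρ).
- Adjusted for baseline: s²(1 − ρ²).
- Difference: s²(1 − ρ)², the regression-to-the-mean part.
- Ratio, adjusted to unadjusted: (1 − ρ²)/[2(1 − ρ)] = (1 + ρ)/2.

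**Step 3: power with log-normal data.** The effect is set so that an unadjusted normal-theory test of d has 80% power: (1.960 + 0.842) × √(1/100 + 1/200) = 0.343 SDs of d. The simulation used 2,500 trials per setting and allocation stratified by patient type. The rank ANCOVA regresses ranked percent change on treatment, ranked baseline and stratum.

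| ρ | (1+ρ)/2 | Adjusted N matching 300 unadjusted | Analytic power, adjusted | Simulated rank-sum | Simulated rank ANCOVA | Gain, points |
|---|---|---|---|---|---|---|
| 0.3 | 0.65 | 195 | 93.5% | 77.9% | 91.8% | 13.9 |
| 0.5 | 0.75 | 225 | 89.9% | 78.5% | 87.2% | 8.7 |
| 0.6 | 0.80 | 240 | 87.9% | 77.0% | 84.9% | 7.9 |
| 0.7 | 0.85 | 255 | 86.0% | 78.0% | 83.3% | 5.3 |
| 0.8 | 0.90 | 270 | 84.0% | 78.6% | 81.7% | 3.1 |

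**Step 4: heavy tails.** Same shifts, with t errors (3 df, scaled to unit variance) on the log scale.

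| ρ | Rank-sum | Rank ANCOVA | Gain, points | Log-scale ANCOVA |
|---|---|---|---|---|
| 0.3 | 94.3% | 99.2% | 4.9 | 93.9% |
| 0.5 | 94.8% | 98.5% | 3.7 | 90.6% |
| 0.6 | 94.0% | 97.8% | 3.8 | 88.6% |
| 0.7 | 95.1% | 97.6% | 2.5 | 86.9% |
| 0.8 | 95.6% | 97.2% | 1.6 | 86.8% |

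**Step 5: a different assumed effect.** A 20% reduction with log-SD 1 (shift −ln 0.8 = 0.223), at ρ = 0.5 / 0.7 / 0.8:
- Log-normal: rank ANCOVA 52 / 68 / 85% v rank-sum 41 / 61 / 81%, gains of 11, 7 and 4 points.
- t with 3 df: rank ANCOVA 71 / 89 / 97% v rank-sum 60 / 85 / 95%, gains of 11, 4 and 2 points. Log-scale ANCOVA has 58 / 76 / 88%.

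**Step 6: size.** In the runs of steps 3 and 4, null rejection was 4.4% to 5.6% for the plain rank-sum test and 4.4% to 5.4% for rank ANCOVA. The Monte Carlo standard error is √(0.05 × 0.95/2500) = 0.44 points, so both are compatible with 5%.

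**Step 7: stratum alone.** A stratified rank-sum test (van Elteren) differed from the plain one by less than 1 point throughout. With an assumed stratum shift of 0.3 SD in the change, at ρ = 0.6, it had 78.6% v 78.1%. Adding baseline as well (rank ANCOVA) gave 85.6%.

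**The case against.** The strongest defence is that the SAP took an option the protocol had already authorised and gave a reason. Protocol 11.6 allows a nonparametric test, Protocol 11.1 lets the SAP govern analysis, and SAP 7.2 defers to the specific section. That stands. A reader might infer a breach of the protocol or a conflict inside the SAP; the documents show neither.

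Moving to ranks was also sound. ANCOVA on raw percent change had less power than the plain rank-sum test in every setting of steps 3 and 4 (for example 62.9% v 78.5% at ρ = 0.5, log-normal). A reader might then take log-scale ANCOVA as the natural replacement. It does slightly better than rank ANCOVA when logs are normal (89.0% v 87.2% at ρ = 0.5). Under the heavy tails of steps 4 and 5 it falls below even the plain rank-sum test, and extreme values are the SAP's stated worry. It also changes the summary measure to a ratio of geometric means.

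The consequences are limited. hsCRP is the last step, so no later test depends on it, and lost power works against the sponsor's own claim. SAP v1.7 records an added hsCRP analysis, and the content of 18.3.4 is not visible. It may hold an adjusted analysis, but that would not alter the test named in 18.2.1 for the hierarchy.

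**Conclusion.** The point holds as a matter of efficiency. A baseline-adjusted rank test had more power than the plain rank-sum test in every setting run: about 3 to 14 points more with log-normal data and about 2 to 11 with heavy tails. These sizes rest on the assumed correlation, spread, tail shape and effect, none of which the documents give. The direction is well supported; the exact size is not. At a correlation of 0.8 the gain is only about 2 to 4 points.

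Three stronger readings are not supported. The test is not invalid, because its size is nominal. Leaving out the stratum is not a material loss by itself, because stratification alone moves power by less than 1 point. Nor has it been shown that the Hodges-Lehmann interval is wider than an adjusted one: no interval widths were computed, and an interval from a log-scale model would be for a different quantity.

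**What to change.** In SAP 18.2.1, before unblinding, name as the confirmatory hsCRP test a rank ANCOVA of percent change to Week 12, with treatment, patient type and ranked baseline hsCRP in the model. Keep the Hodges-Lehmann estimate and confidence interval to describe the size of the effect, and the plain rank-sum test as a sensitivity analysis. Log-scale ANCOVA may be added as supportive but should not lead.

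The cost is a few lines of SAP text and one changed table, with no new data. The small downside is that the p-value and the Hodges-Lehmann interval then come from different procedures and may occasionally disagree; the SAP should say that the rank ANCOVA decides.

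Separately, the section should state whether hsCRP is imputed and, if so, how rank results are combined, since Appendix 4 describes pooling for ANCOVA only. The December 2018 SAP addendum reports that unblinding has taken place, so an adjusted hsCRP result added after that point could only be supportive.

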**18.2.2. OTHER SECONDARY EFFICACY VARIABLES & DERIVATIONS**

Other secondary efficacy endpoints are:

- Change from baseline to Week 12 in LDL-C
- Change from baseline to Week 24 in LDL-C.

The absolute change in LDL-C at week 12, 24 will be summarized using descriptive statistics.

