5.2.2. Secondary Endpoints

1. Percent change from baseline to Week 24 in LDL-C
2. Percent change from baseline to Week 12 in non-HDL-C, TC, apoB, and hs-CRP
3. Absolute change from baseline to Weeks 12 and 24 in LDL-C

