11.6. Secondary and Tertiary Endpoint Analysis

Secondary efficacy endpoints are also of interest for this study, in terms of controlling the overall Type I error rate, a gatekeeping or stepdown approach will be used to test the primary efficacy endpoint and then specific secondary efficacy endpoints sequentially in order to preserve the study-wise Type I error rate. The sequence for the stepdown procedure in this study is as follows:

1. Test the primary efficacy endpoint: percent change from baseline to Week 12 in LDL-C
2. Test the percent change from baseline to Week 24 in LDL-C
3. Test the percent change from baseline to Week 12 in non-HDL-C
4. Test the percent change from baseline to Week 12 in TC
5. Test the percent change from baseline to Week 12 in apoB
6. Test the percent change from baseline to Week 12 in hs-CRP

In this hierarchical testing structure, each hypothesis is tested at a significance level of 0.05, two-sided. Statistical significance at each step is required in order to test the next hypothesis. If the primary endpoint meets the criteria for statistical significance, then the percent change from baseline to Week 24 in LDL-C will be tested; and so forth.

For the remaining secondary efficacy endpoints and the tertiary efficacy endpoints, a significance level of 0.05 will be used; given the large number of remaining endpoints, the p-values for those endpoints will be considered descriptive.

In general, change or percent change in lipid parameters at a given time point will be analyzed using similar ANCOVA model for the primary endpoint with treatment group and patient type (primary prevention; secondary prevention) as factors and the relevant baseline as a covariate.

Baseline for [REDACTED] non-HDL-C, [REDACTED] and TC is defined as the mean of the values from Week -1 (Visit S3) and predose Day 1/Week 0 (Visit T1). Baseline for apoB and hs-CRP is defined as the predose Day 1/Week 0 (Visit T1) value.

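### Absolute LDL-C change, a listed secondary endpoint, loses the protocol's ANCOVA in the SAP and so has no planned treatment difference or confidence interval

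*SAP*

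**What the plan says.** Protocol section 5.2.2 names as its third secondary endpoint "Absolute change from baseline to Weeks 12 and 24 in LDL-C".

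The protocol gives the method twice:

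- The synopsis puts "change from baseline to Weeks 12 and 24 in LDL-C; percent change from baseline to Weeks 12" in a list of endpoints that ends "hs-CRP will each be analyzed using ANCOVA with treatment group and patient type", with the relevant baseline as covariate.
- Section 11.6 states: "In general, change or percent change in lipid parameters at a given time point will be analyzed using similar ANCOVA model for the primary endpoint". It asks for the LSM and SE in each arm, "along with the placebo-corrected LSM, its 95% CI and associated p-value". For secondary endpoints outside the step-down it uses observed data only and treats the p-values as descriptive.

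The SAP classes the endpoint as an other (not key) secondary endpoint, the first entry being "Change from baseline to Week 12 in LDL-C" and the second the Week 24 equivalent. The only analysis sentence in section 18.2.2 is: "The absolute change in LDL-C at week 12, 24 will be summarized using descriptive statistics".

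**The concern.** The two documents plan different analyses of the same listed endpoint, and the one that governs plans less. The LDL-C objectives in protocol sections 5.1.1 and 5.1.2 are comparisons with placebo. Per-arm summaries do not estimate that comparison.

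Baseline adjustment also matters more for absolute change than for percent change. If a drug lowers LDL-C by roughly a constant proportion, the fall in mg/dL is proportional to the starting value. Unadjusted arm means then carry avoidable between-patient variance, and their difference is exposed to chance baseline imbalance. At stake is a prespecified, adjusted treatment effect in mg/dL, with its interval, at each of two visits.

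**Working it through.** The documents state no effect size, SD or power for this endpoint, so there is no plan figure to reproduce. The check is a comparison of texts, followed by an illustration of what the omitted interval would look like.

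**1. Side by side**

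| Item | Protocol (synopsis, 11.6) | SAP |
|---|---|---|
| Status of absolute LDL-C change | Secondary endpoint 3 | Other secondary (18.2.2) |
| Method | ANCOVA: treatment, patient type, baseline | Descriptive statistics (18.2.2) |
| Between-group estimate | Placebo-corrected LSM | None stated |
| Interval | 95% CI | None stated |
| P-value | Reported, descriptive | None stated |
| Missing data | Observed data only | Not addressed for this endpoint |

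**2. Could the SAP's ANCOVA reach this endpoint by another route?** Section 18.1.2 covers the primary endpoint and, for change from baseline in LDL-C, adds descriptive statistics only. Section 18.2.1 extends the model to the key secondary endpoints for LDL-C, non-HDL-C, TC and apoB, all of them percent changes. The Appendix 1 convention for univariate statistics lists n, mean, SD, quartiles, minimum and maximum, with no difference or CI. The tables listed in the December 2018 addendum include none for absolute change.

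**3. Is the departure explained?** Section 18.2.1 justifies its switch to a rank test for hsCRP. Section 18.2.2 gives no reason, and the SAP's modification history does not mention this endpoint. According to Appendix 7 of the protocol (Change 31), the present wording of section 11.6, covering change as well as percent change, came in with Amendment 1, so it is not a leftover from the original protocol.

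**4. Which text governs?** Protocol section 11.1 gives the SAP precedence on data analysis and says the protocol will be amended if appropriate. The current protocol still carries the ANCOVA. The operative plan is therefore the descriptive summary.

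**5. Why baseline matters on this scale.** Take a 20% fall as an illustration, at the LDL-C levels that the documents use as entry thresholds or subgroup cut-points (protocol 6.2.1; SAP 18.2.4):

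- 0.20 × 100 = 20 mg/dL
- 0.20 × 130 = 26 mg/dL
- 0.20 × 160 = 32 mg/dL

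The same proportional effect gives different absolute changes. If ρ is the within-arm correlation between baseline and absolute change, adjustment multiplies the residual SD by √(1 − ρ²). The documents give no ρ, so the gain in precision cannot be put in figures.

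**6. Size of the missing interval.** The inputs are 200 and 100 patients (protocol 6.2) and a two-sided 95% level (SAP 6.5). Assume no missing data and a common residual SD:

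half-width = 1.96 × SD × √(1/200 + 1/100) = 1.96 × SD × 0.1225 = 0.240 × SD

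| Assumed SD (mg/dL) | SE of difference | 95% CI half-width (mg/dL) |
|---|---|---|
| 15 | 1.84 | 3.6 |
| 20 | 2.45 | 4.8 |
| 30 | 3.67 | 7.2 |
| 40 | 4.90 | 9.6 |
| 50 | 6.12 | 12.0 |

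The SDs are assumptions. Over this range the planned sample would give a usable interval.

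**The case against.** The strongest reply has four parts.

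- **The departure is permitted and the loss is small.** The SAP takes precedence, and the section 11.6 rule is hedged as a general one. The same LDL-C values at the same visits are fully modelled as percent change: Week 12 as the primary endpoint and Week 24 as the first step-down secondary. This stands as a limit on importance. It does not supply an adjusted effect in mg/dL, and the synopsis names absolute change in its ANCOVA list without any hedge. The synopsis and section 11.6 differ on imputation for the step-down endpoints, but they agree on observed data for this one.
- **A crude difference and CI can be computed from the arm means and SDs.** That is true, but it would be unadjusted and is not part of the SAP.
- **Not everything is visible.** The output templates mentioned in SAP section 8 are not in the available text, and sections 18.3.3 and 18.3.4 show only headings. An analysis specified there cannot be excluded. Section 18.2.2 nevertheless governs this endpoint, and it says descriptive.
- **The harm is not quantified.** This is fair. Stratification by patient type removes one source of imbalance, baseline LDL-C is tabulated (SAP section 11), and the documents give nothing from which to compute the precision lost.

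**Conclusion.** The concern holds. The governing SAP reduces a listed, comparative secondary endpoint to per-arm description, although the protocol plans ANCOVA for it in two places and no reason is given. Two results, at Weeks 12 and 24, lose their planned placebo-corrected estimate and 95% CI.

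The consequence is limited. The endpoint is outside the step-down sequence (SAP 7.5), its p-values would be descriptive in any case, and no primary or key secondary conclusion changes. It should be corrected, but it does not threaten the trial's validity. The finding itself rests on the text alone; only the illustrative half-widths depend on assumed SDs, full data and equal variances.

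**What to change.** In SAP section 18.2.2, replace the descriptive-only sentence with an ANCOVA of absolute change at Weeks 12 and 24. Use the section 18.1.2 model: treatment and patient type as factors, baseline LDL-C as covariate, and separate residual variances by arm. Run it on observed data in the FAS, as protocol section 11.6 specifies. Report the LSM and SE by arm, the placebo-corrected LSM with its 95% CI, and a p-value labelled descriptive. Keep the descriptive summary alongside.

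The 2018 addendum reports that the planned analyses were completed, so the change may have to be made by a further addendum. That addendum should say that the protocol prespecified the analysis, which separates it from the post-hoc tables.

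The cost is a short text change and two added results from a model already specified for percent change at the same visits. There is no effect on alpha or sample size. If the sponsor prefers to keep the descriptive summary, section 18.2.2 should give the reason and the protocol text should be aligned. That resolves the mismatch but does not recover the estimate.
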